Intervention: Orlistat is the active ingredient while the inactive ingredients include microcrystalline cellulose, povidone, sodium lauryl sulfate, and xylitol. Store at 20-25 °C (68-77°F.) FDA has approved a 60mg dose 3x daily with meals for over-the-counter sale. This is the lowest dose available of Orlistat. Higher doses require a prescription. The dosage will not change during the course of the trial (6 months for each participant). Upon enrollment we will dispense a three-month supply of Orlistat or placebo. At the end of month three they will receive a three-month supply.

Alli (trade name) or Orlistat is a weight loss aid for overweight adults, 18 years and older. It is recommended that Alli be accompanied by a reduced-calorie and low-fat diet and exercise program until weight loss goal is reached. Most weight loss occurs in the first 6 months, hence the 6-month duration of the trial. Participants will be instructed to take 1 capsule (60mg) with each meal containing fat, and not to take more than 3 capsules daily. These are the FDA-approved instructions provided in over-the-counter Alli. Orlistat may decrease absorption of fat soluble vitamins and thus a multivitamin will be provided for all participants to be taken once a day, at bedtime.

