Study staff delivering the intervention will participate in approximately eight hours of training initially with additional training as needed over the course of the study. The training, developed by [name], will include the purpose of the project and will review procedures and materials for use during the study. The PhD student will practice using materials and communicating with others during training. In addition, we will cover confidentiality, listening skills, strategies for coaching (but not directing) and sensitivity to cultural, ethnic, and related issues. During the intervention after obtaining the participants' permission, [name] will patch-in on a random sample of 5% of interactions to assure protocol fidelity and to provide comments to increase the effectiveness of the intervention.

Outcome measures

1. Anthropometric measures / Body composition

Body weight, height and waist circumference (WC) will be measured using procedures based on the most recent NHANES Anthropometry Procedures Manual [11] at the local health department or medical facility at the time of the screening blood draw, 3 month and 6 month blood draws. Briefly, participants will have their weight measured in light clothing without shoes on a regularly calibrated digital scale. Height will be measured using a well-mounted stadiometer. Waist circumference will be assessed in duplicate with a measured tape placed horizontally just above the iliac crest, after completion of a respiratory cycle. When available, we will also measure body composition (% body fat measured by bio-impedance scale). We will compare the initial measurements to the 3-month and 6-month weight measurements.

2. Blood measures

Blood samples will be collected at screening and repeated at 3 and 6 months.

Screening blood samples will be used to determine eligibility but will also be processed and stored for analysis of PBB, PCB, DDT/DDE, and PBDE concentrations with the participants' other study time points. Blood samples will be aliquoted into smaller vials and frozen at -70°C and stored for analysis at the completion of the study.

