The statistical hypothesis of interest is whether a mean change in weight or serum levels of POPs is detected at six months from the baseline. $H_0: \delta_I - \delta_P = 0$ vs $H_a: \delta_I - \delta_P > 0$, testing whether the mean change in weight or serum levels of POPs differs (mean change: δ , between the groups; δ_I , intervention group; δ_P , placebo group). The null hypothesis denotes no mean difference between the groups, and the one-sided alternative hypothesis denotes a difference between the groups, with the intervention group having a greater reduction in weight or serum levels of POPs over the course of the trial.

We plan to recruit and screen PBB registry participants, to enroll 120 participants into the trial. Our goal is to have 100 participants complete the 6-month trial duration. These estimates are based on the power analyses described here:

Power Analysis: The primary objective is to determine if the use of Orlistat results in weight loss in this population. Previous studies have shown an average of 2 to 3 kg weight difference between the intervention and placebo groups [16]. Assuming a standard deviation for weight change of 5 kg, we would have adequate power (80%) to detect a 2-3 kg difference ($\alpha=0.05$; $\rho=0.5$) in weight with a sample size of 50 in each group. Power analyses were performed in PASS 13 software [17].

The secondary endpoint is the change in serum concentrations of PBBs, PCBs, DDE, and PBDE at six months from the baseline. For the outcome of change in serum POP levels, we based our sample size estimations on the historical PBB data for PBB registry participants with at least 2 measurements within a year and the pilot data from Jandacek et al [18]. We estimate that the variance of the differences in PBB levels is expected to be between 0.1 and 0.2 log parts per billion (ppb) (σ^2_{diff}). We have used the pooled variances for our power calculations. From our historical data, we expect a 1% reduction in PBB levels due to the natural course of exposure. A sample size of 50 in each group, would provide at least 80% power to detect a mean change in log PBB levels of -0.1 and -0.2 log ppb with a significance level of $\alpha=0.05$.

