After accounting for 20% attrition (based on 18% in Jandacek), our goal is to recruit at least 60 participants per group. The sample size projections are, in large part dependent on the estimated variances. Given the small sample sizes on which we have to estimate the anticipated variance, there is much uncertainty in the sample size needed. However, given the statistically significant findings of increased excretion of PCBs with only 14 individuals in each group consuming potato chips with artificial fat [18], we feel that 50 individuals in each group comparing Orlistat to placebo is reasonable based on all available preliminary data.

Data Management: Analysis variables will be captured from the study measures (anthropometric measures, blood levels, diet assessment, and physical activity assessment). Data will be collected and coded systematically, reviewed periodically for quality control, logical checks, data entry errors, missing or invalid values and logical inconsistencies among related questions will be checked. Plausibility of outliers will be examined. All data related changes, including changes to respective datasets will be documented electronically. Analytic datasets will be created to address specific study aims. Data dictionaries will be created. All data files will be maintained on a password-protected network system. Original and back-up datasets are stored on a secured network server.

Data exploration and will include the following: 1) determining whether the shapes of continuous distributions indicate that transformations are needed, 2) ensuring that the underlying assumptions of statistical analyses are satisfied (normality, linearity and homogeneity of variance), 3) identifying potential collinearity problems, 4) identifying potential outliers that require further investigation, and 5) exploring bivariate and unadjusted associations with the endpoints and reviewing potential confounding variables. These will be considered prior to constructing models to address our study hypothesis. Descriptive statistics will include means, medians, and percentiles as appropriate for each variable of interest.

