The health history questionnaire (already approved by IRB for the related study IRB# 45959) and an online version of the WHI-PAQ will be created using REDCap Software and available to participants through an online website. The Automated Self-Administered 24-Hour (ASA24) dietary assessment tool will be used to collect information on food consumption over the past 24 hours. Participants will complete the ASA24 at enrollment, 3 months and 6 months. If the participant prefers, the PhD student or authorized staff member will complete the assessments with the participant by telephone. Data from all questionnaires will be reviewed periodically for quality control, data entry errors, logical checks, and inconsistencies among related questions. Plausibility of outliers will be examined. All data related changes, including changes to the datasets will be documented electronically. Analytic datasets will be created to address specific study aims. Data dictionaries will be created. All data files will be maintained on a password-protected network system. Original and back-up datasets are stored on a secured network server.

Exploratory Analyses: Comparisons between the intervention and placebo groups will be conducted to assess the degree to which comparability of study groups was achieved. From the ASA24, we will calculate mean daily caloric, total fat, and carbohydrate intake. We will examine changes in these measures over the study period. From the WHI-PAQ, we will estimate physical activity intensity. Summary tables (descriptive statistics and/or frequency tables) will be provided for all baseline, follow-up, clinical, and exposure data. We will examine longitudinal trends through graphical methods, such as individual profile plots and plots of mean POP levels over time, by group. These plots will be inspected to characterize the within and between subject variations across time.

Statistical Modeling: Data will be analyzed according to the intention to treat (ITT) principle. We will use a repeated measures approach and mixed-effects models [19] where the dependent variable is either body weight in kg or natural-log PBB levels and the primary predictors of interest are the group variable (placebo or intervention) and the measurement time treated as a continuous variable.

The general random-intercept model notation is:

$$Y_{ij} = (\beta_0 + b_i) + (\beta_1 + \beta_2 X_i) t_{ij} + \varepsilon_{ij}$$

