where Y_{ij} denotes the weight in kg or the log-transformed serum PBB concentrations measured on participant i at time t_{ij} where $(i = 1, 2, \dots, n)$ for participants and $(j = 1, 2, \dots, n)$ for measurements within a participant. X_i is an indicator variable which takes the value zero for the placebo group and one for the intervention group. β_0 , represents the overall intercept (mean weight in kg or mean log PBB levels) at baseline, independent of group and b_i is the random effect that represents the deviation from the population mean for participant i . This model assumes that the random effect $b_i \sim N(0, \sigma_b^2)$ and the error $\varepsilon_{ij} \sim N(0, \sigma^2)$ are independent. β_1 and $(\beta_1 + \beta_2)$, represent the slopes (or elimination rates of PBB) for the placebo or the intervention group, respectively. The group-by-time interaction parameter $(\beta_2 X_i * t_{ij})$ assesses if the mean change in weight or if the PBB elimination rates vary by group across time. Slopes that vary randomly among participants will also be considered and an appropriate covariance structure will be selected.

Adjustment for relevant baseline variables and subgroup analyses will be performed to assess differences in weight change or PBB elimination rates by relevant covariates (such as age, gender, initial PBB level, or initial BMI). Since, physical activity reduces body weight and BMI, and increases metabolism, both may be associated with reducing PBB body burden. In multivariable models of serum PBB concentrations, we will consider adjusting for intensity of physical activity and change in BMI in order to measure the independent effect of Orlistat on reducing PBB levels. For the ASA24 measures, we will examine possible associations between changes in mean daily caloric, fat, and carbohydrate intake and serum PBB concentrations. Statistical analyses will be performed in SAS 9.4 software, and models will be fit with the Mixed procedure [19].

DATA & SAFETY MONITORING & REPORTING

Data Safety and Monitoring Plan

OVERSIGHT RESPONSIBILITIES

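### The six-month weight hypothesis is tested only through a straight-line slope, with no pre-specified alternative if weight loss slows after month 3

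*Combined protocol and SAP*

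**What the plan says.** The opening of STATISTICAL ANALYSIS sets the question as "whether a mean change in weight or serum levels of POPs is detected at six months from the baseline", with a one-sided alternative in favour of Orlistat.

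Statistical Modeling answers it with a mixed model for weight in kg or log PBB, with "the measurement time treated as a continuous variable". The displayed equation ("The general random-intercept model notation is") has a common intercept, one slope for placebo and one for Orlistat. The group-by-time coefficient is the only treatment term.

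Three other statements bear on the point:
- Outcome measures: "We will compare the initial measurements to the 3-month and 6-month weight measurements". Weight is therefore seen at three times only: screening, month 3 and month 6.
- Data Management lists, before modelling, "ensuring that the underlying assumptions of statistical analyses are satisfied (normality, linearity and homogeneity of variance"). It does not say what follows if linearity fails.
- Statistical Modeling adds: "Slopes that vary randomly among participants will also be considered and an appropriate covariance structure will be selected".

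On the shape of weight loss, the Intervention section says only: "Most weight loss occurs in the first 6 months, hence the 6-month duration of the trial". Attrition is given as 20% overall, with no figure by arm. No missing-data method or sensitivity analysis is stated beyond the intention-to-treat principle.

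**The concern.** Six times the slope difference equals the month-6 difference only if the arm difference grows in proportion to time. If weight falls quickly and then levels off, two errors follow.

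First, a drug effect that is largely present by month 3 pulls the fitted line up, so its value at month 6 overshoots.

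Second, people seen at months 0 and 3 but not 6 supply only the steep part of the path. If one arm has more of them, its line is steeper and it is credited with weight loss that did not happen. Under a one-sided test this raises the false-positive rate if the arm is Orlistat, and lowers it if the arm is placebo.

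The plan names no curved or categorical alternative. Any change of primary model would be chosen after looking at the data.

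**Working it through.** **The plan's own figure.** Power Analysis claims 80% power for 2-3 kg with 50 per group, SD of change 5 kg and alpha 0.05. The standard error (SE) is 5 x sqrt(2/50) = 1.0, so one-sided power is Phi(D - 1.645): 63.9% at 2 kg, 80.4% at 2.5 kg, 91.2% at 3 kg. The claim is met near 2.5 kg, which I use as the true effect. This calculation compares mean changes and involves no slope.

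**Inputs from the document.** Visits at 0, 3 and 6 months; SD of change 5 kg; 60 per arm; 20% attrition; one-sided 5%.

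**Assumed.** Share f of the six-month loss reached by month 3: 0.5 (linear), 0.7, or 1.0 (full plateau). Visit correlation r: 0.5 to 0.95. Dropout falls after the month-3 visit and is unrelated to outcome. The split by arm and the total loss of 3-4 kg are also assumed.

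**Step 1: expected estimate with equal dropout.** Under a random intercept, the inverse covariance for k visits is proportional to I - cJ, with c = r/(1+(k-1)r). At r = 0.5, c = 1/4 for completers and 1/3 for people with two visits. Let the true arm difference be fD at month 3 and D at month 6. With equal dropout the estimate is 6B/A, where per person:
- completer: A = 45 - 81/4 = 24.75; B = D[(3f+6) - (9/4)(1+f)] = D(3.75 + 0.75f)
- month-3 leaver: A = 9 - 9/3 = 6; B = D(3f - f) = 2fD

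No dropout, f = 1: 6 x 4.5/24.75 = 1.091, so 2.5 kg becomes 2.73 kg.

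20% dropout: A = 0.8 x 24.75 + 0.2 x 6 = 21 and B = D(3 + f), so the factor is 6(3+f)/21. It is 1.000 at f = 0.5, 1.057 at f = 0.7 (2.64 kg) and 1.143 at f = 1 (2.86 kg).

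At r = 0.95 the same algebra gives 2.52 kg (f = 1, no dropout), 2.57 kg (f = 0.7, 20%) and 2.67 kg (f = 1, 20%).

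**Step 2: no drug effect, unequal dropout.** Take r = 0.5, both arms losing 3 kg by month 3 and then flat, 10% placebo and 30% Orlistat leaving after month 3. Averaged per person, the normal equations have these entries:

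| | intercept | cross | slope | right side, intercept | right side, slope |
|---|---|---|---|---|---|
| Placebo | 0.7417 | 2.125 | 22.875 | 1.45 | 12.75 |
| Orlistat | 0.7250 | 1.875 | 19.125 | 1.35 | 11.25 |

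The shared intercept solves to 0.472. The slopes are (12.75 - 2.125 x 0.472)/22.875 = 0.5135 and (11.25 - 1.875 x 0.472)/19.125 = 0.5419. The false difference is 6 x 0.0284 = 0.17 kg. With SE 0.849 kg, type I error is 1 - Phi(1.645 - 0.171/0.849) = 7.4%.

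Over 3-4 kg loss and the correlations examined:

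| Dropout (placebo/Orlistat) | f | False benefit, kg | One-sided type I error |
|---|---|---|---|
| 10%/30% | 0.7 | 0.07-0.11 | 5.9-6.3% |
| 10%/30% | 1.0 | 0.17-0.27 | 7.4-8.6% |
| 15%/25% | 0.7 | 0.03-0.06 | 5.4-5.6% |
| 15%/25% | 1.0 | 0.09-0.14 | 6.1-6.6% |

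Reversing the split reverses the sign. At f = 0.5 the bias is zero. If all leavers go before the month-3 visit it is also zero, because they carry no slope information.

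**Step 3: random slopes.** These change the covariance, not the mean line, and give leavers more weight. With 5 kg loss, f = 0.7 and 10%/30%, the false benefit is 0.11-0.14 kg with a random intercept. It is 0.31-0.37 kg with random slopes when most of the spread in change is put into the slopes; it is smaller when slopes vary less.

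**Step 4: categorical visit.** With arm-by-visit terms the month-6 bias is zero in every scenario above. At 10%/30% the SE goes from 0.849 to 0.880 kg (r = 0.5) and from 0.968 to 0.978 kg (r = 0.9).

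**The case against.** The strongest reply is that neither condition for a material bias is in the document. Saying that most loss occurs in the first six months does not say that it stops at three, and the weight-management text describes gradual dietary change. Attrition is given only overall. Participant Discontinuation or Withdrawal keeps people who stop Orlistat in the study and asks for their month-3 and month-6 procedures. AE Management has those with persistent bowel symptoms stop the drug but continue diet and exercise. The larger payment falls at month 6. All this stands, so the sizes above are conditional.

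A reader might infer that the model doubles each leaver's month-3 loss. It does not. Slopes are pooled by arm and leavers count for less: on within-person slope information, 4.5 against 18 for a completer. A 20% share of leavers therefore carries 0.2 x 4.5/(0.2 x 4.5 + 0.8 x 18) = 5.9% of the arm's slope.

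A reader might also blame early leavers generally. Only departures between months 3 and 6 matter. If half of a 10%/30% dropout comes before month 3, the full-plateau figures fall to 0.09-0.15 kg and 6.2-6.7%.

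Nor is dropout the whole story: at r = 0.5, 2.73 of the 2.86 kg arises with nobody missing.

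The linearity check, the profile plots and the stated comparison with both later weights are real safeguards of a kind. They fall short because none is tied to a named alternative for the primary test, and the plots of means over time are specified for POP levels, not weight.

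**Conclusion.** The point holds in conditional form. The plan asks about month 6 and estimates it through a straight line, with no pre-specified alternative.

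If loss slows after month 3, an early real effect is overstated even with equal dropout: by 0.07-0.14 kg on 2.5 kg at 20% dropout if 70% of it is reached by month 3, and by 0.17-0.36 kg for a full plateau. Unequal dropout after month 3 adds a false difference of about 0.1-0.3 kg at a 10%/30% split under the displayed model, and more with random slopes. Against an SE of 0.85-0.98 kg this is modest.

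The documents do not support the inference that the error will favour Orlistat. They state neither a plateau nor an arm difference in dropout, and more dropout on placebo would make the test conservative.

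The type I error figures assume that the random-intercept covariance is correct. If true slopes vary, a random-intercept model can reject too often even with a linear path; that is a separate matter and is not counted here. The kilogram figures apply to weight. The same mean structure is used for log PBB, for which no size is claimed.

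The change is worth making because it is cheap and removes the dependence on curve shape.

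**What to change.** In Statistical Modeling, enter visit as a categorical factor (0, 3, 6 months) with arm-by-visit terms at months 3 and 6, keeping the common baseline mean. Name the arm difference in change from baseline to month 6 as the primary test. Keep the straight-line slope as a supportive analysis.

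The cost is SAP wording and a little precision. If loss is truly linear and data are complete, the variance of the month-6 effect rises from 0.727 to 0.750 (in units of sigma squared over n) at correlation 0.5, about 3%. At correlation 0.9 it rises from 0.1898 to 0.1900, about 0.1%. With an average of 20% dropout the SE rises by about 1-4%.

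Categorical visit removes the bias from curve shape. It does not protect against dropout that depends on unseen weights.

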Online comprehensive health questionnaire (CHQ) or update of previous health questionnaire		X			
Blood draw for clinical function blood tests (liver, kidney, thyroid); review for eligibility and return results to individuals		X			X
Anthropometry (weight, height, waist circumference)		X		X	X
Blood draw for serum POPs concentrations		X		X	X
Analyses of serum POPs concentrations (baseline, 3 mo., 6 mo.)	After all samples collected				
Randomization			X		
Dietary Assessments			X	X	X
Physical activity assessments			X	X	X
Pill count to check adherence			Months 3, 6		
Compensation			\$40	\$60	
Initiate a weekly telephone call – to answer questions, encourage adherence and determine any adverse events or new health problems – then reduce frequency of calls depending on each patient's needs and preference.			Months 1 -6		
Medication dispensed (Orlistat or placebo)			Enrollment: 3 mo. supply Month 3: 3 mo. supply		
Multivitamins dispensed (200ct)			X		
Post-study follow-up telephone calls			One week and one month after completion		

Study Design Overview: A randomized, double-blind, placebo-controlled 6-month trial will be conducted among selected participants from the PBB Registry. Signed informed consent will be obtained, in person or online, after discussion with study staff and an opportunity to ask questions. Potential participants will be screened for eligibility by self-report of health information and clinical laboratory tests. Study participants will be randomized into one of two groups: the Orlistat (intervention) group or the control (placebo) group. Both groups will be prescribed the same diet and exercise regimen.

Anthropometry measurements (weight, height, waist circumference) will be obtained at enrollment and serum levels of PBB, PCB, DDT/DDE and PBDE (POPs) will be measured at enrollment, at 3 months and at 6 months (all chemical analyses will be done at the conclusion of the trial). We will determine if body weight and serum concentrations of POPs have changed over time in each group. Subgroup analyses by amount of weight loss, enrollment PBB concentration, and gender will be undertaken as well. Data will be analyzed to see if the Orlistat group experiences greater weight loss than placebo and secondarily, whether the Orlistat group experiences a greater reduction in serum POPs over the course of the trial.

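### If initial log PBB is added to the displayed random-intercept model while the enrollment value stays as a response, the one-sided error of that adjusted secondary analysis rises from 5% to about 11%

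*Combined protocol and SAP*

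**What the plan says.** All references are to the combined protocol and SAP.

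- **Measurement times.** Study Design Overview: "serum levels of PBB, PCB, DDT/DDE and PBDE (POPs) will be measured at enrollment, at 3 months and at 6 months".
- **Displayed model.** Statistical Analysis, Statistical Modeling: the response is log PBB at each measurement time. The terms are a common intercept, a time slope, a group-by-time term and a random intercept with independent errors of equal variance. The intercept "represents the overall intercept (mean weight in kg or mean log PBB levels) at baseline, independent of group". Enrollment log PBB is therefore a response, and the equation contains no baseline covariate and no group main effect.
- **Covariance.** The same section then says that random slopes will be considered and a covariance structure chosen.
- **Adjustment.** The next paragraph commits to adjusted and subgroup analyses of weight change or PBB elimination "by relevant covariates (such as age, gender, initial PBB level, or initial BMI"). The Study Design Overview also lists enrollment PBB as a subgroup factor.
- **Test.** The hypothesis is directional ("the one-sided alternative hypothesis denotes a difference between the groups") and the level for PBB is 0.05.

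Nowhere does the plan say what happens to the enrollment row when initial PBB is used as a covariate.

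**The concern.** Adding initial log PBB to the displayed model makes the covariate and the first response the same number. The covariate's coefficient is drawn toward 1 and the enrollment residual toward 0. Both follow-up residuals still carry the enrollment measurement error, so they are correlated with each other but not with the enrollment residual. A random intercept with equal independent errors cannot represent that pattern. It credits the group-by-time estimate with precision that it does not have.

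The adjusted PBB analysis could then report a faster PBB decline on Orlistat about twice as often as the stated 5% when there is none, and its confidence intervals would be too narrow. This happens even if all participants share the same true slope. PBB is a secondary endpoint, but the stated primary objective asks whether weight loss comes with a lower body burden, so readers will look at this analysis.

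**Working it through.** **Inputs from the plan**
- 50 completers per arm, from "A sample size of 50 in each group, would provide at least 80% power".
- Visits at 0, 3 and 6 months, written t = (0, 0.5, 1) in units of six months.
- "We estimate that the variance of the differences in PBB levels is expected to be between 0.1 and 0.2 log parts per billion". Under the random-intercept model the variance of a difference is 2σ², so σ² = 0.05 to 0.10.
- Change under the null of −1% in both arms: "we expect a 1% reduction in PBB levels due to the natural course of exposure".
- One-sided level 0.05.

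**Assumed, because the plan does not give it:** the share of the variance of log PBB that lies between people (ICC), taken from 0.5 to 0.98.

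**Step 1. The plan's own level.** In 15,000 simulated null trials per setting (Monte Carlo SE about 0.26 percentage points), the displayed model rejects one-sided in 4.7 to 5.1%. The stated 5% is reproduced.

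**Step 2. Why adding initial PBB fails.** Take large between-person variation, so that the coefficient on initial PBB is close to 1.
- The residuals are 0, e₁ − e₀ and e₂ − e₀. Their variances are 0, 2σ² and 2σ² (mean 4σ²/3). Their covariances are 0, 0 and σ² (mean σ²/3).
- A random-intercept fit reproduces roughly these averages: intercept variance σ²/3 and error variance 4σ²/3 − σ²/3 = σ². So V = σ²(I + J/3) and V⁻¹ = (I − J/6)/σ², where J is the matrix of ones.
- V⁻¹t = (−0.25, 0.25, 0.75)/σ² and t′V⁻¹t = 0.875/σ². With 100 people coded ±0.5 for group, the sum of squares is 25.
- Variance that the model reports: σ²/(25 × 0.875) = 0.0457σ².
- Actual variance: the weighted residual is −e₀ + 0.25e₁ + 0.75e₂, with variance (1 + 0.0625 + 0.5625)σ² = 1.625σ². This gives 25 × 1.625σ²/21.875² = 0.0849σ².
- SE ratio: √(0.0457/0.0849) = 0.734. One-sided error: P(Z > 1.645 × 0.734) = P(Z > 1.207) = 11.4%.

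σ² cancels, so the plan's range of 0.1 to 0.2 does not matter here. At σ² = 0.05 the reported SE is 0.048 and the actual SE 0.065. In the same limit the displayed model has variance σ²/(25 × 0.5) = 0.08σ², an SE of 0.063. The adjustment appears to gain precision but does not.

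**Step 3. Simulation of the adjusted model** (random intercept, no group main effect, enrollment row kept, 15,000 trials per setting):

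| ICC | 0.5 | 0.7 | 0.8 | 0.9 | 0.95 | 0.98 |
|---|---|---|---|---|---|---|
| One-sided error, % | 10.6 | 10.5 | 10.9 | 11.0 | 11.1 | 11.2 |

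At ICC 0.9 the model SE is 0.047 against an actual 0.063, a ratio of 0.746, or 25% too small. Then P(Z > 1.645 × 0.746) = P(Z > 1.227) = 11.0%, which agrees with the table. With 60 per arm and one-sixth dropping out, the error is 10.8 to 12.3%.

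**Step 4. What changes the result**

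| Variant | One-sided error, % |
|---|---|
| Covariate-by-time term also added | 10–12 |
| Initial PBB as a median split | 6–8 |
| Group main effect added, complete data | 4.1–5.2 |
| Group main effect added, with dropout | 5.4–6.0 |
| Random slopes fitted in the adjusted model (250 runs) | about 5–6 |
| Separate earlier PBB value as covariate | 4.7–5.5 |
| Baseline as covariate, months 3 and 6 only as responses | 3.9–5.5 |

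**The case against.** The strongest reply is that the inflation needs a particular combination that the plan never states as such: a continuous log covariate, the enrollment row kept, a random intercept only, and no group main effect.

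- **Covariance selection.** The plan says random slopes will be considered. If the structure is chosen on the adjusted model, AIC preferred random slopes in every simulated trial, and the error after selection was 4.2 to 6.3%. This is a real safeguard, but it depends on the order of work. The text puts the covariance choice before adjustment. When the structure was chosen on the unadjusted model and initial PBB was then added, AIC kept the random intercept about 90% of the time and the error was still about 11%.
- **Group main effect.** The text names group as a primary predictor, so an analyst might add it, and that restores about 5%. The displayed equation leaves it out and describes the intercept as common to both groups.
- **Wording.** Initial PBB is one example in a list that covers two outcomes and both adjustment and subgroup analyses. The eligibility text also accepts a PBB level from the previous five years, and using such a separate value causes no material inflation. This stands, and it makes the point conditional. But the plan says that adjustment will be done, and the enrollment value is the most natural reading of an initial level.

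A reader might infer that the trial's main PBB test is invalid. The documents do not support that: the displayed model has no such covariate and holds about 5%, and nothing makes the adjusted model the main test. A reader might also infer an error of 13% or more. That size appears only if true slopes vary (12.1 to 13.7% at slope SDs of 0.15 to 0.22), and the displayed model is then already at 6.4 to 8.4%.

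**Conclusion.** The point holds as a conditional one. Under the displayed random-intercept equation, adding continuous initial log PBB while keeping the enrollment row makes the group-by-time standard error about 25% too small. The one-sided error rises from 5% to about 11% (10.5 to 12%). The result rests on the displayed error structure, 50 per arm, three visits and an assumed ICC; the ICC hardly matters between 0.5 and 0.98. The random-slope result comes from only a few hundred runs per setting, so it shows that most of the inflation goes but not the exact remaining rate.

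Severity: should fix. It concerns an adjusted analysis of a secondary endpoint. But whether that analysis is valid now turns on choices the plan leaves open, and the literal reading is one that fails.

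**What to change.** State in Statistical Modeling that baseline log PBB enters the PBB model once, in one of two ways:

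1. as the first response, with no initial-PBB covariate (the displayed model); or
2. as a covariate, with only the month-3 and month-6 values as responses.

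Apply the same rule to each other pollutant in its own model, and to the subgroup analyses by enrollment PBB. Those analyses can stay; they only need the second form. If the first form is kept, take initial PBB off the list of adjustment covariates for the PBB model. It may stay as a covariate for weight.

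Both forms bring the one-sided error back to about 5% (4.7 to 5.1% and 3.9 to 5.5%). The cost is one or two sentences, with no new data and no change to recruitment. All pollutant assays are to be run after the last sample is collected, so the choice can be fixed before any PBB result exists.
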